9.2 Sample Size and Randomization

Precision analysis. Because we are estimating an effect size, rather than a p value, we are primarily concerned with precision of estimation rather than power. The standard deviation associated with total grief as measured with the MM-CGI is around 35.78 raw units. Thus, a change of one SD represents a two-thirds of a unit change in the MM-CGI Likert Scale. If we obtain a sample of 64 participants per condition, our standard error of measurement (SEM) around this effect size estimate will be about 4.47 units, producing confidence intervals between -8.77 and +8.77 units. This will allow us to estimate a Cohen's d within .25 SD units of the actual value, a reasonably robust estimate, 95% of the time. Adjusting for a 10% attrition rate, we will collect a total sample of 72 participants per condition (a total of 144 participants).⁵⁷

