9 STATISTICAL CONSIDERATIONS

9.1 General Design Issues

CGMI-V is a Stage I longitudinal randomized clinical trial. ADRD caregivers whose family members are in long-term care facilities (LTCFs) will be recruited, screened for inclusion criteria, and randomly assigned to either CGMI-V or a Minimal Treatment (MT) control condition. Caregivers in the CGMI-V condition will participate in eight weekly professionally led, real-time, live-streaming video online group sessions. Those caregivers in the MT control condition will receive written information materials about late-stage ADRD at baseline. For both conditions, data will be collected at baseline (pre-intervention), 8 weeks (immediately post-intervention) for intervention effects, and 24 weeks post baseline for maintenance effects. The design for this study was chosen to avoid the type of group clustering or contamination that would be engendered by the use of a randomized cluster design. The study hypotheses are outlined below:

Primary Hypothesis

Hypothesis 1: We hypothesize that caregivers in the CGMI-V condition compared to those in the MT control condition, will report decreased chronic grief levels.

Secondary Hypotheses

Hypothesis 2: We hypothesize that caregivers in the CGMI-V condition compared to those in the MT control group will report (2.1) decreased symptoms of depression and anxiety and (2.2) increased positive mental states.

Hypothesis 3.1 and 3.2: We hypothesize that caregivers in the CGMI-V condition compared to those in the MT control condition will report (3.1) increased satisfaction with care provided in the facility and (3.2) decreased conflict with staff.

Mechanism of Intervention Hypothesis

Hypothesis 4: We hypothesize that CGMI-V works by changing the exacerbators of chronic grief: lack of knowledge, sense of loss, guilt, and role captivity.

Primary Outcome Measures

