Caregiver Chronic Grief will be measured with the 50-item Marwit-Meuser Caregiver Grief Inventory (MM-CGI).⁶ This inventory has three subscales: (1) *Personal Sacrifice Burden*: 18 items measuring individual losses experienced as a result of caregiving, (2) *Heartfelt Sadness and Longing*: 15 items measuring interpersonal emotional reactions in response to caregiving, and (3) *Worry and Felt Isolation*: 17 items measuring feelings of losing connections with, and support from, others. Items are rated on a 5-point scale (1 = *strongly disagree* to 5 = *strongly agree*), with a possible range of 50 to 250 points. Grief scores may be calculated by subscale and then added to formulate a total grief score. Total grief scores above 175 indicate high levels of caregiver grief, requiring formal intervention and support. Cronbach's alpha subscale scores range from .90 to .96, indicating high internal consistency reliability for each subscale and for their combined total grief score. Test-retest Cronbach's alpha scores range from .71 to .75, indicating stability of the measure over time in all three subscales.¹⁵

Secondary Outcomes Measures

Depressive symptoms will be measured with the 20-item version of The Center for Epidemiological Studies Depression Scale (CES-D).⁴⁰ Responses are based on a four-point frequency rating (0 = *rarely or none of the time* to 3 = *all of the time*), with a possible range of 0 to 60. A score above 16 indicates existence of depressive symptoms. Internal consistency reliability range $r = .85$ to $.90$, and test-retest reliability $r = .45$ to $.70$.⁴⁰

Anxiety symptoms will be measured with the 20-item State-Anxiety subscale of the State-Trait Anxiety Inventory (STAI).⁴¹ Responses are based on a scale of 1 to 4 (1 = *almost never* to 4 = *almost always*), with a possible range of 20-80, where higher scores indicate greater anxiety. Alpha coefficients for older adults range .90-.92, indicating high internal consistency reliability.⁴¹

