9.5 Data Analyses

We will track all study participants following CONSORT guidelines and enter all data into a REDCap database. SPSS for Windows (Version 22) and R (Version 3.1.1) will be used for data management and statistical analysis. A two-tailed 0.05 significance level will be used for all statistical tests except where noted below. All analyses will be performed on an intent-to-treat basis. Missing data will be imputed using the R mi package, a multiple imputation computer program based on the work of Rubin.

Histograms will be obtained for these variables, and skew and kurtosis will be assessed to assess statistical normality. From previous research, we expect the error rates to have statistically normal distributions or distributions that can be transformed to normality using logarithmic and square root transformations. We will perform any necessary transformations using Tukey's ladder of transformation before conducting statistical analysis. Because these trials are designed to estimate precise effect sizes rather than probability values, the results of each trial will be the effect size (comparing treatment and control groups) and confidence intervals around this estimate.

Aim 1. Controlling for background variables, establish effect sizes of the CGMI-V condition and Minimal Treatment (MT) control condition on changes in a primary caregiver chronic grief outcome.

Multilevel linear models will be run for the CGMI-V and MT control conditions. Multilevel models are used to estimate autocorrelation across the three time points. We hypothesize that chronic grief will decrease more in the CGMI-V condition relative to the MT control condition. Caregiver sex, age, relationship to the care-receiver, as well as care recipient death or discharge from the facility, will be controlled for as covariates in the analysis. Sex and caregiver/care recipient relationship, as well as care recipient death or discharge from the facility, will be entered into the model as dummy-coded variables. We will examine the interaction effects (δ) to make certain that they are large

enough to justify a more robust clinical trial. While there is some likelihood of obtaining significant findings in this study, the primary purpose of this analysis is to estimate effect sizes.

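### Section 9.2's precision (SE 4.47, ±8.77 units, d within .25 SD) is that of one arm's mean; on the same inputs the unadjusted two-arm difference has SE 6.33, ±12.4 units, ±0.35 SD

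*Combined protocol and SAP*

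**What the plan says.** Section 9.2 sets out a precision argument and no power calculation: "we are primarily concerned with precision of estimation rather than power". It gives two inputs. One is the spread of the primary outcome, "The standard deviation associated with total grief as measured with the MM-CGI is around 35.78 raw units". The other is 64 evaluable participants in each condition, raised to 72 (144 in total) for 10% attrition. From these it concludes that "our standard error of measurement (SEM) around this effect size estimate will be about 4.47 units, producing confidence intervals between -8.77 and +8.77 units", and then: "This will allow us to estimate a Cohen's d within .25 SD units of the actual value", at 95% confidence.

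Section 9.5 says what the effect size is. The results of the trial "will be the effect size (comparing treatment and control groups) and confidence intervals around this estimate". The primary analysis is a multilevel linear model over baseline, 8 weeks and 24 weeks, with caregiver sex, age, relationship, and care recipient death or discharge as covariates. On how the result will be used, it says "We will examine the interaction effects (δ) to make certain that they are large", and the sentence goes on to make this the test of whether a fuller trial is warranted.

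Section 9.1 separates the two follow-ups by purpose: "8 weeks (immediately post-intervention) for intervention effects, and 24 weeks post baseline for maintenance effects". It also reports, for the MM-CGI subscales, that test-retest "scores range from .71 to .75, indicating stability of the measure over time in all three subscales". Section 9.2 does not refer to those values.

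**The concern.** The stated precision is attached to a between-arm effect size, but it has the form SD/√n with n the size of one arm. A difference between two independent means carries the sampling error of both. On the same SD and the same n its standard error is therefore √2 times larger, unless some feature of the analysis reduces it, and Section 9.2 names no such feature.

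This matters because precision is the only numerical support given for 144 participants. The interaction effects will also be used to judge whether a larger trial is justified, so readers need to know how wide the margin around them is likely to be. The documents set no numerical threshold for that judgement.

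**Working it through.** **Inputs.** SD 35.78, 64 evaluable per arm, 95% confidence (all Section 9.2); 1:1 allocation (Section 9.2.1); effect size defined as treatment against control (Section 9.5).

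**Reproducing the plan's figures.**
- SD/√n = 35.78/√64 = 35.78/8 = 4.4725
- 1.96 × 4.4725 = 8.77 units
- 8.77/35.78 = 0.245 SD

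All three stated figures are recovered with no further assumption. Other simple choices do not match: pooling all 128 gives SE 3.16; 72 per arm gives 4.22 for one arm and 5.96 for two; a t quantile on one arm gives ±8.94. The attrition step is sound: 64/0.9 = 71.1, rounded up to 72.

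**The two-arm figure on the same inputs.**
- SE = 35.78 × √(1/64 + 1/64) = 35.78 × √(2/64) = 6.33
- 1.96 × 6.325 = 12.4 units
- 12.40/35.78 = 0.346 SD

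Chance that this estimate lies within .25 SD of the true value: 0.25 × 35.78/6.325 = 1.414, and 2Φ(1.414) − 1 = 0.843. To reach ±0.25 SD with this unadjusted contrast would take 2 × (1.96/0.25)² ≈ 123 evaluable per arm.

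**Could the planned model recover ±8.77?** The documents give no baseline-to-follow-up correlation for the total score, so r below is an assumption. It is taken as equal between all pairs of time points. Each half-width is 12.40 × √(variance factor), in MM-CGI units.

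| Two-arm contrast | Variance factor | r = 0.5 | r = 0.71 | r = 0.75 | r needed for ±0.25 SD |
|---|---|---|---|---|---|
| One follow-up, change score | 2(1 − r) | ±12.4 | ±9.4 | ±8.77 | about 0.74 |
| One follow-up, baseline-adjusted | 1 − r² | ±10.7 | ±8.7 | ±8.2 | about 0.69 |
| Mean of both follow-ups, change score | 1.5(1 − r) | ±10.7 | ±8.2 | ±7.6 | about 0.65 |
| Mean of both follow-ups, baseline-adjusted | (1 + r)/2 − r² | ±8.8 | ±7.3 | ±6.9 | about 0.46 |

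The last contrast is never wider than ±9.3 units (±0.26 SD) for any r ≥ 0. A change score at one follow-up is wider than ±12.4 when r is below 0.5: at r = 0.3 it is ±14.7.

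The stated ±8.77 can therefore arise from a two-arm contrast, but only with a contrast and a correlation that Section 9.2 does not state. Over r from 0.5 to 0.75 the options run from ±6.9 to ±12.4.

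**The case against.** Four points can be made for the plan.

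1. **Some wording suits a per-condition effect.** Section 3 and Aim 1 in Section 9.5 speak of effect sizes for each condition on changes in grief. A within-arm change at r = 0.5 has SE 35.78 × √(2 × 0.5)/√64 = 4.47. The wording is indeed loose. But a Cohen's d, and the explicit definition in Section 9.5, point to a comparison of arms, and the stated hypothesis is comparative.

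2. **The unadjusted difference is not the planned analysis.** This stands. The factor of √2 and the 84% apply to that contrast only, and the multilevel model may do better. If the subscale test-retest values of .71 to .75 carried over to the total score, one follow-up would give ±8.2 to ±9.4, close to what is stated. However, Section 9.2 does not invoke those values, and stability over 8 to 24 weeks under an intervention is unknown.

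3. **±12.4 is not an upper bound.** This also stands. Baseline grief is not among the listed covariates, and a time-by-condition interaction with baseline as an outcome can behave like a change score, which is wider than ±12.4 if r is below 0.5. Delivery in groups of up to six, in the CGMI-V arm only, could widen it as well. With an assumed intraclass correlation of 0.01 to 0.10, SE = 35.78 × √((1 + 5 × ICC)/64 + 1/64), giving ±12.6 to ±13.9. These points affect how the corrected paragraph should be written. They do not rescue the present one.

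4. **The consequence is small.** In a Stage I trial meant to estimate effect sizes, the reported interval will come from the data and no decision rule changes. That limits the weight of the point, but the figure is still the stated basis for the sample size.

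**Conclusion.** The concern holds. For a comparison of two arms, Section 9.2's precision is wrong as written: it is a one-arm standard error presented as that of the effect size. The size of the discrepancy for the unadjusted difference rests only on the plan's own SD and n. Any narrower or wider figure depends on a contrast and a correlation that the documents leave open.

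The finding is limited to the planning statement. It does not show that ±0.25 SD is out of reach, and it gives no reason to change the sample size.

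**What to change.** Keep 144 participants and rewrite the precision paragraph in Section 9.2:

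- **Give the two-arm reference figure**, for example: with 64 evaluable caregivers per arm and an SD of 35.78, the standard error of the unadjusted difference between arms is 6.33 MM-CGI units, giving a 95% confidence interval of ±12.4 units, or about ±0.35 for Cohen's d.
- **Name the contrast that the precision refers to**: 8 weeks, 24 weeks or an average of both, and change from baseline or baseline-adjusted. If a figure other than the reference is claimed, state the assumed correlation and its source and show a range. For one follow-up and r from 0.5 to 0.75, the range is ±12.4 to ±8.77 units for a change score and ±10.7 to ±8.2 for a baseline-adjusted contrast. For the baseline-adjusted mean of both follow-ups it is ±8.8 to ±6.9.
- **If the values in Section 9.1 are the source**, say that they are subscale test-retest figures. It would also help to say whether clustering by video group has been allowed for.
- **Correct the term.** The quantity is a standard error of the difference. A standard error of measurement describes the error in an individual's score.

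The cost is one paragraph, with one named contrast and one stated correlation where needed. Recruitment, data collection and the analysis model stay as they are.

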9.2.1 Treatment Assignment Procedures

The study is a Stage I longitudinal randomized clinical trial. ADRD caregivers whose family members are in LCTFs will be recruited, screened for inclusion criteria, and randomly assigned to either CGMI-V or a Minimal Treatment (MT) control condition. Randomization will be stratified in six Waves of 24 participants each, to insure that there are exactly 12 participants in each condition. In Wave 1, we will randomly assign the first 24 enrolled participants to either the CGMI-V condition ($n = 12$; 6/group) or MT control condition ($n = 12$). The same process will continue for the next five Waves. Recruiters and data collectors will be blinded as to the random assignment of each participant. Once caregivers sign the consent to enroll in the study, the Project Director will use randomization software to assign each enrolled participant to CGMI-V or the MT condition. The Project Director will then inform the participants directly of their assignments and ask them to maintain confidentiality about their assignment at data collection points.

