4.3 Study Enrollment Procedures

Recruitment. Successful recruitment strategies used in our prior studies²⁵⁻²⁷ will be used. These include: (1) a notice describing the study placed in the providers' monthly newsletters distributed to family caregivers at each facility; (2) study flyers and interest forms posted around the LTCFs (e.g., front desk, family lounge); (3) individualized letters mailed by the facilities' business office introducing the project to family caregivers of ADRD residents; and (4) oral presentations about the project to staff and family caregivers during "family night" events. All written and oral communication will use lay language to describe study purpose, eligibility criteria, intervention, and data collection methods. All written materials will include information about participants' time commitment and study contact information (e-mail address and phone number) that caregivers may use if interested. Interested participants will call or e-mail the study office or fill out the interest form, agreeing to be contacted by study staff. Completed interest forms will be left in the facility's front office or e-mailed directly to the study e-mail address.

Consenting. After they contact the study office, caregivers will be scheduled to undergo eligibility screening. The Project Director will describe the screening process and the instruments used to screen and will ask and document caregivers' verbal consent to be screened for eligibility. Once eligibility is determined, participant caregivers will be

informed of the next steps for enrollment in the study. Study staff will use a Web-based tracking system, Microsoft Access, to document individual reasons for ineligibility and reasons for declining participation in caregivers who met eligibility criteria. Caregivers who meet the inclusion criteria will be sent paper or electronic copies of the study informed consent form for examination. Within the next 24-48 hours, a telephone appointment with the PI or the Project Director will be scheduled to answer any questions caregivers may have about the study prior to obtaining informed consent. If agreeable to join the study and depending on how they preferred to receive the informed consent forms, caregivers will return the signed documents either electronically (e-signature) or in paid, study self-addressed envelopes.

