Randomization. The study will be implemented in six waves. Beginning in Month 5 of the study, we will start recruiting and enrolling 24 eligible caregivers for Wave 1, who will be randomly assigned to either the CGMI-V condition ($n = 12$; 6/group) or MT control condition ($n = 12$) using a randomization software for clinical trials. After these 24 caregivers have been enrolled, the study team will start recruiting an additional 24 caregivers for Wave 2. There will be a total of six waves. Each wave will have 8 weeks to recruit, screen, and complete baseline data collection, followed by 8 weeks to implement the intervention condition, and 24 weeks from baseline follow-up. Once enrollment is completed for a wave, recruitment and randomization will start for the following wave. This pattern will be the same for all six waves. This will result in 144 caregivers being enrolled, 72 for the CGMI-V condition, and 72 for the MT control condition (Figure 1).

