6.2.1 Screening Evaluation

Consenting Procedure

The Project Director will schedule a phone or online screening interview with caregivers expressing an interest in the study. The Project Director will explain the screening process and the questionnaires used to ascertain participant eligibility and invite any caregiver questions. After all questions are addressed, verbal consent to screening will be documented after the screener explicitly asks the caregivers if they consent.

Screening

Caregivers who verbally consent will be screened using computer-assisted telephone interviewing (CATI) for the following inclusion criteria:

- 21 years of age or older
- Identified as family member, fictive kin (self-identified family member) or partner of care recipient
- Within the first two years of care recipient's permanent placement in a long-term care facility (LTCF)
- Care recipient is a resident in a dementia or memory care unit in the LTCF, where a diagnosis of ADRD is mandatory
- Possessing self-reported basic computer literacy and in-home internet access
- Able to speak, read, and write English
- Not currently attending another ADRD caregiver grief management group
- Experiencing high to moderate levels of grief per screening with the Marwit-Meuser Caregiver Grief Inventory-Short Form³⁸ (scores 25 or above), and/or experiencing high levels of depressive symptoms per screening with PHQ9³⁹ (scores 10 or above)

Caregivers meeting all eligibility criteria will be sent a consent form including detailed information about the study. A phone or online meeting will be scheduled with the PI or the Project Director within the next 24-48 hours for discussion of study,

content of consent form, and to respond to any other questions.

Enrollment

Participants will be enrolled into the study once their signed study informed consents are being returned to study office. A baseline appointment will be scheduled within the next 24-48 hours.

Baseline Assessments

Participants who are enrolled into the study, will be assessed at baseline using CATI, for the following outcomes:

- Caregiver and care recipient socio demographics
- Caregiver and care recipient situational characteristics
- Caregiver grief
- Caregiver depressive symptoms
- Caregiver anxiety symptoms
- Caregiver positive states of mind
- Caregiver conflict with facility staff
- Caregiver satisfaction with care in the facility
- Caregiver knowledge of ADRD
- Caregiver sense of loss
- Caregiver guilt

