10 DATA COLLECTION AND QUALITY ASSURANCE

10.1 Data Collection Forms

Trained Research Assistants (RAs) blinded to treatment condition will use Computer-assisted Telephone Interviewing (CATI) to complete all initial screening and data collection interviews. Study RAs will read each question and enter the response directly into the secure, web-based Research Electronic Data Capture (REDCap).

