11.2 Informed Consent Forms

All written and oral communication will use lay language to describe study purpose, eligibility criteria, intervention, and data collection methods. All written materials will include information about participants' time commitment and study contact information (e-mail address and phone number) that caregivers may use if interested. Interested participants will call or e-mail the study office or fill out the interest form, agreeing to be contacted by study staff. These forms will be left in the facility's front office or e-mailed directly to the study e-mail address. After they contact the study office, caregivers who meet the inclusion criteria will be sent paper or electronic copies of the informed consent and HIPAA forms for examination. Within the next 24-48 hour, a telephone appointment with the PI or the Project Director will be scheduled to answer any questions caregivers may have about the study prior to obtaining informed consent. If agreeable to join the study, and depending on how they preferred to receive the forms, caregivers will return the signed documents either electronically (e-signature) or in paid, study self-addressed envelopes. Recruitment will be overseen by the PI and the Project Director. In facilities with African American residents, recruitment will be overseen by [name] (Co-I), who has expertise in recruitment of participants of diverse backgrounds.

A signed consent form will be obtained from each participant. The consent form will describe the purpose of the study, the procedures to be followed, and the risks and benefits of participation. A copy will be given to each participant and this fact will be documented in the participant's record.

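### Allocation is not concealed from the Project Director, who deals with caregivers before consent and also runs the randomisation and announces each arm

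*Combined protocol and SAP*

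**What the plan says.** All references are to the combined protocol and SAP.

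- **Blinding (9.2.1):** "Recruiters and data collectors will be blinded as to the random assignment of each participant".
- **Assignment (9.2.1):** after consent is signed, the Project Director runs the software for each enrolled caregiver and then tells them the arm.
- **Balance (9.2.1):** "Randomization will be stratified in six Waves of 24 participants each, to insure that there are exactly 12 participants in each condition".
- **First contact (6.2.1):** "The Project Director will schedule a phone or online screening interview with caregivers expressing an interest in the study". Sections 4.3 and 6.2.1 also have this role explain screening; 4.3 has it ask for and document verbal consent to be screened.
- **Before written consent (4.3; similarly 6.2.1 and 11.2):** "a telephone appointment with the PI or the Project Director will be scheduled to answer any questions".
- **Oversight (11.2):** "Recruitment will be overseen by the PI and the Project Director".
- **Who interviews (10.1):** Research Assistants blinded to arm use computer-assisted telephone interviewing "to complete all initial screening and data collection interviews".
- **Concealment:** section 4.3 mentions only that randomisation software will be used. No independent holder of the sequence, sub-blocks or other concealment step is described.

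**The concern.** Allocation concealment protects the period before a caregiver commits to the trial. Anyone who talks to caregivers in that period should not be able to foresee the next arm. Here one role has pre-consent contact and also sees every assignment. Because each wave must end at exactly 12 and 12, knowing the earlier assignments says something about those that remain.

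Waves follow one another, so a caregiver could be encouraged, discouraged or left for the next wave with a likely arm in mind. Willingness to attend an eight-session group is an obvious basis for such selection, and it is not among the covariates in section 9.5. Outcomes are self-reported by participants who know their arm. The trial's product is an effect size meant to inform a larger trial, so any selection bias would carry forward.

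**Working it through.** **1. Does the blinding statement hold for the Project Director?** By 4.3, 6.2.1 and 11.2 the role has scheduling, explanatory, verbal-consent and oversight duties in recruitment, and may hold the pre-consent call. By 9.2.1 it makes and announces the assignments. For this role the statement fails. No section shows Research Assistants or other recruiters being given assignments, so the failure is shown for this role only.

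**2. When is assignment made?** The text supports two readings.
- *One at a time.* Section 9.2.1 ties assignment to the signing of consent. The schedule in 6.1 puts randomisation in the enrolment column, ahead of baseline. Control caregivers are due their written materials at baseline (sections 3 and 5.1), the baseline appointment is arranged within 24–48 hours of enrolment (6.2.1), and a wave has 8 weeks to fill (section 3). On that timetable an early enrollee's arm would be needed before the wave closes.
- *Batch.* Section 9.2.1 also speaks of randomly assigning the first 24 enrollees as a set, and 6.2.1 lists randomisation after the baseline assessments.

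The first reading has more support, but the text does not settle it.

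**3. The plan's totals.** 6 × 24 = 144 and 6 × 12 = 72 per arm, as section 4.3 states: "This will result in 144 caregivers being enrolled, 72 for the CGMI-V condition, and 72 for the MT control condition". The sample size is not in question.

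**4. Predictability if assignment is one at a time.** Assume one random block per wave with n = 12 places per arm, no sub-blocks, and all earlier assignments in the wave known.
- Expected allocations certain in advance: 2n/(n + 1) = 24/13 = 1.85 per wave; × 6 = 11.1 of 144.
- By position, the chance of certainty is 1.00 for the 24th, 0.48 for the 23rd, 0.22 for the 22nd, 0.09 for the 21st and 0.04 for the 20th.
- Expected correct guesses when choosing the arm with more places left: n + (4^n / C(2n, n) − 1)/2 = 12 + (16,777,216/2,704,156 − 1)/2 = 12 + (6.204 − 1)/2 = 14.60 of 24, or 60.8%. Over six waves that is 87.6 of 144, against 72 by chance.
- Exact enumeration gives the same totals. Mean accuracy is 54.4% over the first 12 places, 67.3% over the last 12 and 74.2% over the last 6.

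**5. Predictability if assignment is a batch draw.** If all 24 have consented before the draw, 0 allocations are foreseeable before consent and guessing stays at 50%.

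**The case against.** The strongest reply is that someone must know the arm in order to notify participants, that 9.2.1 names recruiters and the Project Director separately, and that overseeing recruitment is not recruiting. Screening interviews belong to blinded Research Assistants under 10.1, the PI may hold the consent call, and 9.2.1 can be read as a batch draw, which would remove the predictability. Entry rests on scored cut-offs for grief and depressive symptoms and on self-reported computer literacy, which leaves limited room for steering. Baseline grief is one of the three modelled time points, so selection on grief severity is at least partly absorbed.

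Much of this stands, and it rules out several stronger inferences a reader might draw.
- *That recruiters and data collectors generally are unblinded.* No section shows this.
- *That the Project Director conducts the screening interviews.* Section 10.1 gives them to Research Assistants; 4.3 and 6.2.1 give the Project Director scheduling, explanation and verbal consent.
- *That 11 of 144 allocations will be known in advance.* This needs one-at-a-time assignment, an unsplit block and a known tally.
- *That the analysis has no protection against baseline differences.* Section 9.5 adjusts for sex, age, relationship and care-recipient death or discharge, and baseline grief is modelled. Unmeasured motivation is what remains unprotected.

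The reply does not remove the central point. Taking verbal consent to screening and possibly holding the pre-consent call are direct contacts, not oversight, and the plan does not separate them from knowledge of the arms.

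**Conclusion.** The point holds for the Project Director. The plan as written lets a person with pre-consent contact see the assignments, contrary to the blinding stated in 9.2.1 if that role counts among the recruiters, as its duties imply. Predictability ranges from 0 certain allocations and 50% guessing (batch draw after all 24 consent) to about 1.85 per wave, or 11 of 144, and 61% guessing (sequential, unsplit 12:12 block, tally known). Even at the upper end most allocations are only more guessable, mainly late in a wave. These figures measure predictability, not bias: the documents give no basis for estimating an effect on grief scores. The plan should be changed, at modest cost.

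**What to change.** In 9.2.1, have the Statistician or the Data Manager generate and hold the sequence and run the assignment. Both roles exist in 10.2 with no recruitment contact described; state that they will have none.

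That alone is not enough, because the Project Director would still learn each arm when announcing it or mailing control materials. Add one of the following:
- **Batch release.** Draw and release a wave's 24 assignments together once all 24 have consented and completed baseline. This keeps 12:12 per wave and N = 144, and nothing is foreseeable before consent.
- **Separated roles.** Keep anyone who knows earlier arms in an open wave out of that wave's pre-consent contacts: scheduling and explaining screening, verbal consent and the consent call. This avoids delay but moves work from the Project Director. The PI could take the consent call only if also unaware of the arms in that wave.

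Cost: protocol wording and software access rights, with no added staff or participants. Batch release has a real downside. Early control enrollees could receive their materials up to about 8 weeks after their baseline assessment, close to their 8-week assessment. The text on delivery at baseline and the anchor for the 8- and 24-week assessments would have to be reconciled. Intervention groups may face the same wait while a wave fills.

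Under either option, state whether assignment is sequential or by batch, and reconcile 9.2.1 with 4.3, 6.1, 6.2.1, 10.1 and 11.2 on who screens, who discusses consent, who knows the arms, and whether randomisation precedes baseline.
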